 - If AST and ALT are $<2x$ ULN on repeat testing, resume dosing at the next expected interval.
 - If AST and ALT are not $<2x$ ULN by 4 weeks, permanently discontinue study treatment.
- Note: Three independent temporary suspensions from study treatment due to transient elevations in ALT and/or AST $\geq 2x$ but $\leq 3x$ ULN is allowed during the entire treatment period. If a third elevation occurs that requires a dose to be held, permanently discontinue study treatment.
- A Significant Infection.
 - *Defined as:*
 1. Any severe infection meeting SAE criteria as defined in Section 12, or
-

2. Any infection not meeting SAE criteria but otherwise clinically significant per investigator's judgment, *or*
 3. Infection or reactivation of EBV or CMV as defined by clinical signs of infection; or if the EBV viral load is $\geq 10,000$ copies per mL plasma or the CMV viral load is $\geq 10,000$ copies per mL plasma.
- Suspend administration of study treatment and recheck any abnormal laboratory values as soon as possible and preferably within 72 hours.
 - Monitor the subject and abnormal labs at least weekly.
 - If the AE resolves or reduces to mild or less, dosing may resume at the next expected interval.
 - If the AE does not resolve in 4 weeks, permanently discontinue study treatment.
 - A Serious Adverse Event or Study Agent-related Severe Adverse Event.
 - *Defined as:*
 1. Any SAE (as defined in Section 12.1.1) *or*
 2. Any severe AE that is considered related (possibly, probably, or very likely related) to study agent (as defined in Section 12.1.2).
 - With the exception of:

When clinical and laboratory abnormalities are considered related to T1D disease activity (ie, hypoglycemia and hyperglycemia) and study treatment is not considered a contributing factor, administration may not need to be modified. The site investigator should consult with the sponsor if this is encountered.
 - Suspend administration of study treatment and recheck the subject at least weekly; if based on abnormal laboratory values, repeat abnormal laboratory values as soon as possible within 72 hours.
 - If the AE resolves or reduces to a moderate AE (Section 12.1.2) or less, dosing may resume at the next expected interval.
 - If the AE does not resolve to a moderate AE or less (Section 12.1.2) in 4 weeks, discontinue study treatment permanently.

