12.1.2. Severity Criteria

An assessment of severity grade will be made using the following general categorical descriptors:

- **Mild:** Awareness of symptoms that are easily tolerated, causing minimal discomfort and not interfering with everyday activities.
- **Moderate:** Sufficient discomfort is present to cause interference with normal activity.
- **Severe:** Extreme distress, causing significant impairment of functioning or incapacitation. Prevents normal everyday activities.

The investigator should use clinical judgment in assessing the severity of events not directly experienced by the subject (eg, laboratory abnormalities).

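### Protocol 10.2: a significant infection that is mild but unresolved at 4 weeks meets both the resume rule and the permanent-stop rule

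*Protocol*

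**What the plan says.** Protocol 10.2, under temporary and potentially permanent discontinuation, defines a significant infection in three ways: a severe infection meeting the criteria for a serious adverse event (SAE); another infection that the investigator judges clinically significant; and an EBV or CMV event. The third begins "Infection or reactivation of EBV or CMV as defined by clinical signs of infection; or if the EBV viral load is" at least 10,000 copies per mL of plasma, with the same limit for CMV. Clinical signs and viral load are alternatives, so either can start the hold.

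Four instructions then apply to all three types:

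- Start: "Suspend administration of study treatment and recheck any abnormal laboratory values as soon as possible and preferably within 72 hours".
- During the hold: "Monitor the subject and abnormal labs at least weekly".
- Resume: "If the AE resolves or reduces to mild or less, dosing may resume at the next expected interval".
- Stop: "If the AE does not resolve in 4 weeks, permanently discontinue study treatment".

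The list of permanent-discontinuation events earlier in 10.2 includes meeting the infection criteria of this block, so the stop bullet is binding.

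Section 12.1.2 defines mild as "Awareness of symptoms that are easily tolerated, causing minimal discomfort and not interfering with everyday activities". The same section leaves the severity of events that the subject does not directly experience, such as laboratory abnormalities, to the investigator's clinical judgment.

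**The concern.** The resume bullet can be met in two ways: resolution, or reduction to mild or less. The stop bullet mentions only the first. Between them lies an ordinary clinical course, an infection that improves to mild and lingers, for which the text both permits dosing and requires that it end for good.

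The second difficulty is specific to EBV and CMV. When the hold begins on a laboratory value alone, the reader needs to know what that value must do before dosing resumes or stops. The bullets speak only of the adverse event and its severity, and for a laboratory-only event severity is a matter of judgment. The required rechecks produce results that no decision rule uses.

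What is at stake is consistent safety handling and consistent exposure across sites. Protocol 9.6 schedules CMV and EBV PCR to detect an effect of the study agent on these infections, so this part of the stopping rules should read the same way everywhere.

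**Working it through.** No power, sample-size or error-rate figure enters this point, and the plan states no number to reproduce. The check is to apply the bullets literally at the 4-week mark, with the neighbouring SAE/related severe AE block as a control. That block resumes at moderate or less, and its stop bullet reads "If the AE does not resolve to a moderate AE or less (Section 12.1.2) in 4 weeks, discontinue study treatment permanently".

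| AE status at 4 weeks | Infection: may resume | Infection: must stop | Both | SAE block: may resume | SAE block: must stop | Both |
|---|---|---|---|---|---|---|
| Resolved | yes | no | no | yes | no | no |
| Mild | yes | yes | **yes** | yes | no | no |
| Moderate | no | yes | no | yes | no | no |
| Severe | no | yes | no | no | yes | no |

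Viral load appears in neither infection bullet, so splitting each row into load below 10,000 and load at or above 10,000 gives 4 × 2 = 8 states with the same answers. The results are:

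- Infection block: 2 of 8 states (mild, either load) meet both rules.
- SAE/related severe AE block: 0 of 8.
- ALT/AST block: below 2 × ULN resumes, and not below 2 × ULN by 4 weeks stops. Conflicts: 0 of 2 states.

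A worked case: an infection falls to mild at 2 weeks, and dosing may resume at the next interval. At 4 weeks it is still mild and not resolved, and the stop bullet now requires permanent discontinuation. Viral load plays no part, so the overlap covers all three infection types.

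For the load-triggered hold, four of the eight states have load still at or above 10,000. Read literally, the resume bullet is met in two of them (resolved and mild). The resolved state is doubtful, because an infection defined by its load is hardly resolved while the load persists. That doubt itself shows that the text does not say what resolution means for such an event.

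Doses at stake in the double-blind period (every 2 weeks, Weeks 0 to 52):

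- Total: 52/2 + 1 = 27, as Protocol 7.1.1 states.
- PCR visits with doses still to come, from the Time and Events Schedule: Weeks 12, 26 and 38.
- Doses after Week 12: (52 − 14)/2 + 1 = 20.
- Doses after Week 26: (52 − 28)/2 + 1 = 13.
- Doses after Week 38: (52 − 40)/2 + 1 = 7.

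So a permanent stop following the Week 12 result forgoes at most 20 of 27 doses. If the subject had resumed and taken 2 doses within the 4 weeks before being stopped, the loss would be 20 − 2 = 18.

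**The case against.** The strongest reply is that the bullets are meant in sequence: subjects who improve may resume, and those still on hold at 4 weeks stop. The unresolved condition in the stop bullet would then be shorthand for failing the bullet above it. That may well be the intent, but the text does not say so. The resume bullet treats resolution and reduction to mild as separate outcomes, and the next block spells out its stop condition in full. That the resume bullet is permissive does not help either, since discretion to resume does not cancel a mandatory stop.

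A second reply is that a laboratory trigger with a clinically judged release is a legitimate design choice. That stands: using different measures to start and end a hold is not in itself a contradiction. What remains is that the bullets do not say how the rechecked load counts.

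A reader might go further and infer that an asymptomatic subject above the viral-load limit can be graded mild on the first day and so be released at once. The documents do not support this. The resume bullet requires the event to resolve or reduce, and an event mild from the start has not reduced. Section 12.1.2 leaves the grading of laboratory-only events to judgment. While the load stays at the limit, definition item 3 and its instruction to suspend can be read as still in force.

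There are also safeguards. Under 10.2 the investigator may discontinue treatment permanently for safety, and 9.6 provides for blinded sponsor review and an unblinded data monitoring committee. These limit the harm but do not make the rule consistent.

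**Conclusion.** The contradiction is real and general: any significant infection that is mild but unresolved at 4 weeks meets both rules in Protocol 10.2. Separately, for a hold started by EBV or CMV load, the role of the rechecked load in resuming or stopping is not stated. The first conclusion rests on reading the two bullets as written; it would fall away if the sponsor confirmed the sequential reading in the text. The second would remain.

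The number of subjects affected cannot be estimated, because the documents give no frequency for significant infection or for EBV/CMV reactivation. The figure of 20 of 27 doses is an upper limit for one subject stopped after the Week 12 PCR result. It cannot be combined with doses resumed during the 4-week window in the same subject.

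A reader might infer that the Week 52 C-peptide comparison is at risk. Without an event frequency that is unsupported. In addition, 10.2 encourages subjects who stop treatment to keep all scheduled visits, and SAP 5.3.2 analyses them as randomized. This is a defect in a stopping rule that sites must apply consistently, not a demonstrated threat to the primary result.

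**What to change.** In Protocol 10.2, under A Significant Infection, the sponsor should reconcile the resume bullet and the 4-week bullet so that no subject can meet both. It should also reconcile those bullets with the viral-load trigger in definition item 3, so that sites know how the rechecked load bears on resuming or stopping. Which threshold, measure or clinical rule should govern is for the sponsor to decide; no view is taken here.

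The cost is a few lines of wording and a memo to sites, issued through the formal amendment that Protocol 17.1 requires. The reconciliation need not add a test, because 10.2 already requires rechecks and at least weekly monitoring of abnormal laboratory values during the hold.

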10.3. Withdrawal From the Use of Research Samples

A subject who withdraws from the study will have the following options regarding the optional research samples:

The collected samples will be retained and used in accordance with the subject's original separate informed consent/assent for optional research samples.

The subject may withdraw consent/assent for optional research samples, in which case the samples will be destroyed, and no further testing will take place. To initiate the sample destruction process, the investigator must notify the sponsor study-site contact of withdrawal of consent/assent for the optional research samples and to request sample destruction. The sponsor study-site contact will, in turn, contact the biomarker representative to execute sample destruction. If requested, the investigator will receive written confirmation from the sponsor that the samples have been destroyed.

Withdrawal From the Optional Research Samples While Remaining In The Main Study

The subject may withdraw consent/assent for optional research samples while remaining in the study. In such a case, the optional research samples will be destroyed. The sample destruction process will proceed as described above.

Withdrawal From The Use Of Samples In Future Research

The subject may withdraw consent/assent for use of samples for research (refer to Section 16.2.5, Long-Term Retention of Samples for Additional Future Research). In such a case, samples will be destroyed after they are no longer needed for the clinical study. Details of the sample retention for research are presented in the main ICF.

11. STATISTICAL METHODS

Statistical analysis will be done by the sponsor or under the authority of the sponsor. A general description of the statistical methods to be used to analyze the efficacy and safety data is outlined below. Specific details will be provided in the Statistical Analysis Plan (SAP).

Descriptive statistics (eg, mean, median, standard deviation [SD], minimum, and maximum) will be used to summarize continuous variables. Counts and percentages will be used to summarize categorical variables. Graphic data displays may also be used to summarize the data.

Efficacy analyses will be based on the modified intent-to-treat (mITT) population (ie, all randomized subjects who have received at least 1 dose of study agent). Subjects included in the efficacy analyses will be summarized according to their assigned treatment group regardless of whether or not they receive the assigned treatment.

Safety analyses will include all subjects who received at least 1 dose of study treatment.

Pharmacokinetics and immunogenicity analyses for golimumab will include all subjects who receive at least 1 dose of golimumab and have at least 1 post-dose sample collection.

The baseline measurement is defined as the closest measurement taken at or before the time of the Week 0 administration for the double-blind period. The baseline measurement for the open-label extension period is the closest measurement taken at or before the time of the Week 0 administration of the open-label extension period.

No hypotheses testing will be performed for open-label extension period, and data generated will be summarized descriptively.

11.1. Subject Information

For all subjects who receive at least 1 dose of study agent, descriptive statistics will be provided. Subject baseline data, demographic, and baseline clinical disease characteristics will be summarized for all mITT subjects.

11.2. Sample Size Determination

The sample size calculation is based on the primary endpoint, an MMTT 4-hour C-peptide AUC at Week 52. Due to skewed C-peptide AUC data, normalizing transformation of $\log(AUC + 1)$ is applied for sample size assessment. The method has been well accepted and used in numerous clinical studies^{25,26,42,57,60}. Based on published data, a common SD of $\log(AUC + 1)$ of 0.215 is assumed, and the back-transformed means for 4-hour C-peptide AUC are assumed to be 0.385 and 0.635 for the placebo and golimumab groups respectively, ie the expected treatment difference (back-transformed) is 0.25. With 81 subjects (54 on golimumab and 27 on placebo) and an alpha of 0.05 (2-sided), there is 90% power to detect the treatment difference through a 2-sample t-test.

11.3. Efficacy Analyses

All efficacy analyses will be performed on the mITT population unless otherwise specified. The mITT population includes all randomized subjects who have received at least 1 dose of study agent. The primary efficacy endpoint will be analyzed by using a mixed model for repeated measures (MMRM).

Primary Endpoints

The primary endpoint is the MMTT-stimulated 4-hour C-peptide AUC at Week 52. To address the primary objective of the study, the primary endpoint will be analyzed by using a MMRM based on restricted maximum likelihood. The model will be based on a normalizing transformation of $\log(\text{AUC}+1)$. The analysis will use post-baseline $\log(\text{AUC}+1)$ data as the response variable and will include the fixed, categorical effects of gender, treatment, time, and treatment-by-time interaction, as well as the continuous, fixed covariates of baseline and baseline-by-time interaction. An unstructured covariance will be used to model the within-patient errors. The treatment comparison at Week 52 in terms of the least square mean difference and the 2-sided 95% confidence interval will be estimated based on this model. Descriptive statistics and estimates from the above model will be presented on the back-transformed scale. Specifically, the back-transformed mean is the geometric-like mean derived through $\exp(y)-1$, where $y = \log(\text{AUC}+1)$. For transparency and completeness, descriptive statistics on the raw scale will be presented as well. Additional details will be presented in the SAP.

To assess the robustness of the primary analysis result, some sensitivity analyses will be conducted. Such analyses include but are not limited to the following:

1. Similar repeated measure analysis with some data imputed. If a subject's last observed AUC value prior to Week 52 is 0, then all missing values through Week 52 will be imputed with zero. Repeated measure analysis will be conducted on the partially imputed data.
2. An analysis of covariance (ANCOVA) model with $\log(\text{AUC}+1)$ at Week 52 as the response variable, baseline $\log(\text{AUC}+1)$ and age as covariates, and treatment and gender as fixed factors. Different missing data handling strategies such as completers' analysis, and multiple imputation will be explored.
3. Similar ANCOVA model by using different transformation functions.
4. Comparing change from baseline in 4-hour C-peptide AUC directly by using non-parametric method such as rank analysis of covariance or ANCOVA model if the normality assumption holds.

Subgroup analysis of the primary endpoint by selected baseline characteristics will be presented. Details will be outlined in the SAP.

Secondary Endpoints

The major secondary endpoints listed below will be analyzed without multiplicity adjustment. Treatment effect in these endpoints will be estimated by the difference between the treatment

groups along with their associated 95% confidence intervals. The hypoglycemia event rate (number of hypoglycemia episodes per patient-year exposure) at Week 52 will be analyzed using a Poisson regression model. Change from baseline in insulin use and change from baseline in HbA1c will be analyzed by using an MMRM model. Additional details will be provided in the SAP.

1. Change from baseline in insulin use in units per kilogram body weight per day at Week 52.
2. Change from baseline in HbA1c at Week 52.
3. Hypoglycemic event rates (defined as BG levels of ≤ 70 , 55, and 35 mg/dL or clinical sequelae consistent with severe hypoglycemia in the absence of a BG reading) through Week 52.

11.3.1. Exploratory Efficacy Analyses – Open-Label Extension Period

All the efficacy endpoints defined for the double-blind period will be exploratory for the open-label extension period and will be summarized descriptively. Disease progression will be compared between the double-blind period and the extension period in subjects who attended the open-label extension period if deemed reasonable.

11.4. Pharmacokinetic Analyses

Data will be listed for all subjects with available serum concentrations per treatment. All concentrations below the lowest quantifiable concentration (LQC) in a sample or missing data will be labeled as such in the concentration data listings. Concentrations below the LQC in a sample will be treated as 0 in the summary statistics and for the calculation of PK parameters. All subjects and samples excluded from the analysis will be clearly documented in the study report.

For each dose group, descriptive statistics, including arithmetic mean, SD, coefficient of variation, median, minimum, and maximum will be calculated for the golimumab serum concentrations at each sampling time of golimumab.

Serum golimumab concentrations will be summarized over time. In addition, if necessary, a population PK analysis will be performed to characterize the PK of golimumab as well as to identify and quantify important covariates of PK in the T1D population. The apparent total systemic clearance (CL/F) and apparent volume of distribution (V/F) will be estimated using a NONMEM approach and will be presented in a separate technical report.

The same analyses will be performed for the open-label extension period.

11.5. Immunogenicity Analyses (Antibodies to Golimumab)

The occurrence and titers of antibodies to golimumab during the study will be summarized over time for all subjects who receive an administration of golimumab and have appropriate samples collected for detection of antibodies to golimumab (ie, subjects with at least 1 sample obtained after their first golimumab administration).

The incidence of neutralizing antibodies (NAbs) to golimumab will be summarized for subjects who are positive for antibodies to golimumab and have samples evaluable for NAbs to golimumab.

Other immunogenicity analyses may be performed to further characterize the immune responses that are generated.

The same analyses will be performed for the open-label extension period.

11.6. Biomarker Analyses

Results from exploratory analyses will be presented in a separate biomarker technical report.

The same analyses will be performed for the open-label extension period.

11.7. Pharmacokinetic/Pharmacodynamic Analyses

If data permits, the relationships between serum golimumab concentration and efficacy may be analyzed graphically. If a visual trend is observed, a suitable PK/PD model may be developed to describe the exposure-response relationship and will be presented in a separate technical report.

The same analyses will be performed for the open-label extension period.

11.8. Pharmacogenomic Analyses

For the double-blind period, results from exploratory and haplotype analyses will be presented in a separate biomarker technical report.

For the open-label extension period, results from the exploratory analyses will be presented in a separate biomarker technical report.

11.9. Safety Endpoints and Analyses

Safety assessments will include the examination of the incidence rates of AEs, vital signs, laboratory parameters, and physical examinations. Safety analyses will be conducted on the safety analysis set, which is defined as all subjects who have received at least a 1 dose of study agent.

Adverse Events

The verbatim terms used in the CRF by investigators to identify AEs will be coded using the Medical Dictionary for Regulatory Activities (MedDRA). Treatment-emergent AEs are AEs with onset during the treatment period or that are a consequence of a pre-existing condition that has worsened since baseline. All reported treatment-emergent AEs will be included in the analysis. For each AE, the percentage of subjects who experience at least 1 occurrence of the given event will be summarized by system organ class and preferred term for treatment group. Treatment-emergent AEs will also be summarized by a maximum severity and relationship to study agent. Separate summaries will be provided for SAEs and AEs leading to study agent discontinuation.

In addition, summary tables will be presented by treatment group for each of the endpoints within each specified period:

Double-Blind Period:

- a. Proportion of subjects with treatment-emergent AEs and severe AEs through Weeks 52 and 104.
- b. Proportion of subjects with study agent injection site reactions through Week 52.
- c. Proportion of subjects with severe infections through Weeks 52 and 104.
- d. Open-Label Extension Period:
 1. Continue to evaluate safety and exploratory efficacy endpoints as per the [Time and Events Schedule](#) (open-label extension period) and no new efficacy hypotheses will be tested compared to the double-blind period.

Listings, datasets, or subject narratives may be provided, as appropriate, for those subjects who die, who discontinue treatment due to an AE, or who experience a severe or an SAE.

Clinical Laboratory Tests

Laboratory data will be summarized by type of laboratory test. Reference ranges and markedly abnormal results (specified in the SAP) will be used in the summary of laboratory data. Descriptive statistics will be calculated for each laboratory analyte at baseline and for observed values and changes from baseline at each scheduled timepoint. Frequency tabulations of the changes from baseline will be presented in pre- versus post-treatment cross-tabulations (with classes for below, within, and above normal ranges). Frequency tabulations of the abnormalities will be made. A listing of subjects with any markedly abnormal laboratory results will be provided.

Vital Signs

Descriptive statistics of temperature, pulse/heart rate, respiratory rate, and blood pressure (systolic and diastolic) values and changes from baseline will be summarized at each scheduled timepoint. The percentage of subjects with values beyond clinically important limits will be summarized and a corresponding listing will be provided.

Physical Examination

Proportion of subjects with abnormal physical examination findings will be summarized at each scheduled timepoint. Subjects with any post-treatment abnormalities will be listed.

Open-Label Extension Period

Clinical laboratory tests, vital signs, and physical examination for the open-label extension period will be assessed as similar to the double-blind period.

